1 BACKGROUND INFORMATION AND RATIONALE

Bronchopulmonary Dysplasia affects up to half of very preterm infants, yet little is known about how this condition is best managed in the outpatient setting, especially in the time immediately following discharge from the neonatal hospitalization. The proposed trial will be the first study of oxygen saturation targeting for infants with established BPD and the first study to evaluate the efficacy and safety of home oxygen saturation targeting for this vulnerable population.

1.1 Introduction

Bronchopulmonary dysplasia (BPD) is most commonly defined as oxygen dependence at 36 weeks postmenstrual age. BPD affects nearly half of surviving extremely preterm (<28 weeks gestational age) infants, and the incidence of BPD has increased over time. Infants with BPD face more than doubled odds of death after 36 weeks PMA or disability at 5 years compared to preterms without BPD. BPD is associated with abnormal lung function throughout childhood and significantly increases health care costs. Cognitive and respiratory outcomes are closely linked throughout the life course; thus, optimal long-term management of BPD during infancy may ultimately improve cognitive outcomes of this high-risk population.

Supplemental oxygen is a lifesaving therapy for premature infants; yet, there is limited evidence to guide the use of supplemental oxygen beyond the immediate newborn period. The American Thoracic Society (ATS) has been quite definitive in stating that “oxygen is increasingly viewed as a safe and relatively convenient means for maximizing growth and development” in infants with BPD. But supplemental oxygen also carries potential risk, as it is implicated in the causal pathway for morbidities such as retinopathy of prematurity (ROP). In addition, targeting high oxygen saturations (SpO₂) with supplemental oxygen may be associated with increased pulmonary oxygen toxicity and decreased quality of life, without improving neurologic outcomes. In the absence of sound evidence to guide medical decisions, there is currently a significant variation in practice with regard to use of oxygen therapy in this population. No controlled studies have evaluated the safety or efficacy of supplemental oxygen for improving outcomes of infants with established BPD. This is a critical knowledge gap in neonatal and pediatric pulmonary medicine. This study will test whether targeting higher versus lower oxygen saturations in infants with BPD influences rates of hypoxemia and clinical outcomes during the first 6 months of life.

1.2 Name and Description of Investigational Product or Intervention

The intervention that will be tested in the current study is higher versus lower oxygen saturation target ranges for infants with established BPD.

1.3 Relevant Literature and Data

Several recently published randomized trials have compared oxygen saturation (SpO₂) target ranges for extremely preterm infants immediately after birth, up to only 36 weeks PMA. These trials have differing methodology and conflicting results.(1-3) Two older trials compared SpO₂ target ranges for slightly older preterm infants. The BOOST trial randomized 358 preterm infants who were *oxygen dependent at 32 weeks* to higher (95-98%) or standard (91-94%) saturation target ranges. (4) Participants remained on the study intervention until oxygen was discontinued: a median of 2.5 weeks in the standard target group and 5.7 weeks in the high target group. Only about half of the infants still required supplemental oxygen at 36 weeks. The BOOST Trial did not demonstrate any

benefits associated with targeting higher SpO₂ in this population. The STOP-ROP multicenter trial randomized 649 infants with pre-threshold retinopathy and a median SpO₂ of <94% to conventional oxygen targets (SpO₂ 89-94%) and supplemental oxygen targets (96-99%). (5) These targets were continued for two weeks or until the infants met the ophthalmologic endpoint of the study, whichever occurred later. STOP-ROP was stopped early for futility and a loss of equipoise in favor of the high saturation arm. The adjusted odds ratio for progression to threshold retinopathy in the supplemental arm as compared to the conventional arm, which was the primary outcome of the trial, was 0.72 (95%CI 0.52-1.01). In these trials, there were no differences between the groups in growth at 36 weeks or 12 months (BOOST) or 2 months (STOP-ROP). (4,5) In summary, RCTs in the acute newborn period up to 36 weeks have conflicting results; and studies from 32-36 weeks show no benefit but potential harm. Crucially, no trials have compared the impact of prolonged SpO₂ targeting for very preterm children with moderate or severe BPD after 36 weeks.

Secondary analyses of a large randomized trial comparing higher versus lower SpO₂ targeting for newborn extremely preterm infants (6) demonstrated that IH, and in particular events <80% for at least one minute, are common in this population between birth and at least 9-10 weeks of age. (7) The duration of time with SpO₂ <80% is associated with the combined outcome of death after 36 weeks or disability at 18 months, cognitive or language delay, motor impairment, and severe retinopathy of prematurity. Importantly, this effect is significantly stronger when IH occurs 9- 10 weeks after birth than when it occurs earlier. While the neonatal community has been striving to minimize events in the weeks prior to discharge, these data force us to evaluate the value of reducing IH throughout infancy. It is unknown whether infants with BPD continue to have IH after 36 weeks PMA or after hospital discharge, or whether ameliorating this with longer-term use of supplemental oxygen would improve outcomes of these high-risk infants. IH is an important and novel therapeutic target in BPD, and may be a key component of decisions regarding safe and appropriate use and weaning of supplemental oxygen.

A recent trial of late caffeine therapy enrolled infants who were at least 33 PMA and in room air. (8) The control group had an average of 8.4 episodes of intermittent hypoxemia (decline in SpO₂ by at least 5% from baseline to <90% and lasting at least 5 seconds) per hour at 35 weeks PMA, which declined to 3.0 events per hour at 39 weeks PMA. The total time spent with saturations <90%, <85%, and <80% declined dramatically between 35 and 39 weeks. The clinical relevance of these more minor IH episodes and periods of hypoxia have not yet been demonstrated.

Our study collaborators have developed a simple, low-cost device for the BPD STAR Trial that securely transmits oximetry data wirelessly from the home environment. This device will enable us to implement a novel approach to studying management and outcomes of BPD. This study will provide critical data about whether infants with BPD continue to have IH after discharge; whether targeting higher SpO₂ ameliorates IH; and whether this management strategy is associated with improved outcomes until 6 months of age.

1.4 Compliance Statement

This study will be conducted in full accordance all applicable Children's Hospital of Philadelphia Research Policies and Procedures and all applicable Federal and state laws and regulations including 45 CFR 46 and the Good Clinical Practice: Consolidated Guideline approved by the

International Conference on Harmonisation (ICH). All episodes of noncompliance will be documented.

The investigators will perform the study in accordance with this protocol, will obtain consent and assent, and will report unanticipated problems involving risks to subjects or others in accordance with The Children's Hospital of Philadelphia IRB Policies and Procedures and all federal requirements. Collection, recording, and reporting of data will be accurate and will ensure the privacy, health, and welfare of research subjects during and after the study.

2 STUDY OBJECTIVES

The purpose of this study is to test whether targeting higher, as compared to lower, oxygen saturations reduces the incidence of IH and improves clinical outcomes for preterm infants with established BPD.

2.1 Primary Objective

The primary objectives of this study are to compare the incidence of intermittent hypoxemia (defined as: SpO₂ <80% for >=30 seconds) and total duration of hypoxemia between 36 weeks PMA and 6 months corrected age among infants with BPD randomized to higher versus lower SpO₂ target ranges.

2.2 Secondary Objectives

The secondary objectives are to describe clinically relevant outcomes over the first 6 months in the two study groups. These outcomes include quality of life, respiratory health-related resource utilization, feeding, and growth.

3 INVESTIGATIONAL PLAN

3.1 General Schema of Study Design

The proposed study will be a randomized clinical pilot trial. Enrolled infants with moderate or severe BPD will be randomized to higher or lower oxygen saturation (SpO₂) target ranges, which will be maintained until 6 months corrected age.

The two SpO₂ target groups represent the currently accepted range of clinical practice. Therefore, neither group is labeled as “intervention” or “control.”

Please reference Table 1 above for an overall visual explanation of study procedures. The study procedures will be discussed in detail in section 4.

3.1.1 Screening- Baseline

Potential subjects will be screened using the protocol inclusion and exclusion criteria. Parental/guardian permission (informed consent), will be obtained prior to any study related procedures being performed. Randomization occurs when infants have been extubated. However, parents of infants who are on higher levels of support, may be approached to introduce the study. Consent will be obtained at time of extubation. Once the infant meets all eligibility criteria (, the

subject will be randomized to higher or lower oxygen saturation (SpO₂) target ranges and study monitoring (3.1.2) will begin.

3.1.2 Phase 1 – Inpatient monitoring

After randomization, the alarm settings on the standard hospital equipment will be adjusted according to the participant's group assignment. The study SpO₂ ranges are similar to the standard of care ranges in the CHOP NICU, where the clinical alarms for infants born <30 weeks are 95% (high) and 87% (low) until 36 weeks PMA. After 36 weeks PMA, alarms are set at 98% (high) and 90% (low). Participants will continue on the study-mandated alarm settings until discharge to home.

In addition, participants will be placed on the study monitor in order to facilitate collection of study data. This is similar to the approach previously used in the CHOP and HUP NICUs for the Canadian Oxygen Trial. Nurses will be instructed to follow alarms from the clinical monitors, not the study monitor, while the infant is in the NICU. Per standard of care, the infant will be on the clinical monitor continuously. Every effort will be made to also keep the infant on the study monitor continuously; however, it is sufficient to have minimum of 4 days per week/8 hours per day of data. This is consistent with the minimum planned data collection planned for the outpatient phase of the study.

If patients are reintubated, oxygen saturation targets will be at the discretion of the clinical team. However, they will be encouraged to maintain the study mandated targets.

3.1.3 Phase 2 – Outpatient monitoring

At the time of hospital discharge, as detailed below, families will be given a Masimo oximeter along with a device that will transmit the oximetry data back to the study team at CHOP. They will be instructed how to use the device nightly while the child is sleeping at home.

Infants who are discharged per clinical recommendations on supplemental oxygen will have frequent visits in the CHOP Pulmonary Clinic. Oxygen titration and weaning will be standardized according to the algorithm in Table 2, below.

Table 2: Home Nasal Cannula Flow Titration Algorithm*		
	HIGHER SpO₂ TARGET ARM ($\geq 96\%$)	LOWER SpO₂ TARGET ARM ($\geq 90\%$)
Criteria for INCREASING O ₂ flow rate	SpO₂ < 96% for > 10% of recorded time	SpO₂ < 90% for > 10% of recorded time
Criteria for MAINTAINING current O ₂ flow rate	SpO₂ $\geq 96\%$ for 90-95% of recorded time	SpO₂ > 90% for $\geq 90\%$ of recorded time but NOT > 94% for $\geq 90\%$ of recorded time
Criteria for WEANING O ₂ flow rate	SpO₂ $\geq 96\%$ for >95% of recorded time	SpO₂ > 94% for $\geq 90\%$ of recorded time

*Decisions will be made by assessment of recorded oximetry. A minimum of 4 days of data, with a minimum of 8 hours per day, will be required for analysis to make a wean. Oxygen flow rates will be decreased stepwise: 2 LPM – 1.5 LPM – 1 LPM – 1/2 LPM – 1/4 LPM – 1/8 LPM. Once the child is stable on 1/8 LPM, he/she will be weaned off for increasing duration of time: first 6 hours, then 12 hours per day, and finally off completely.

Downloaded oximetry data will be reviewed and decisions about weaning will be made each week by the study team (including [name] from the Division of Pediatric Pulmonology). In the home setting, weans may be performed as often as every week. If an infant loses >5% of body weight in any month, no oxygen weans will be made until the weight is regained. If an infant is discharged without oxygen or weans off but then meets the criteria for increasing flow on two subsequent recordings, the family will be instructed to attend pulmonary clinic for assessment and then home oxygen therapy will be instituted.

3.1.4 Phase 3 – 3 and 6 month corrected age outcomes assessment

Per standard of care, participants will be evaluated in the CHOP Neonatal Follow-up Program at 3 and 6 months corrected ages. Several study outcomes, clinical outcomes in particular, will be assessed during these clinical visits. Based on the limited existing literature, average age of weaning from supplemental oxygen in infants with BPD is between 2-4.5 months corrected age.(9,10) For the current study, the oxygen titration protocol and study oximetry will continue until 6 months corrected age, with the expectation that nearly all participants will have weaned to room air by the end of the study period. If participants remain on oxygen after the conclusion of the study, the pediatric pulmonologist primarily responsible for the child's ongoing BPD care will make decisions about further weaning. For all other participants, ongoing clinical care will be provided by the neonatal follow-up clinic and pediatrician.

3.2 Allocation to Treatment Groups and Blinding

Infants will be randomized to higher or lower oxygen saturation (SpO₂) target ranges. The randomization sequence will be determined in advance, stratified by gestational age (<27 and 27-29 6/7 weeks at birth) and severity of BPD (moderate or severe, see Table 3 below) and balanced in random blocks of 2 or 4 patients. Allocation will be concealed in sequentially numbered opaque envelopes. The envelope with the lowest number will be opened by study staff. This plan for allocation concealment and stratification by key biologic variables will protect the scientific rigor of the study. After randomization, study group assignments will not be blinded. Multiples will be randomized separately. The two target SpO₂ ranges in the current trial represent the middle and upper range of the currently accepted range of clinical practice in our center.

Table 3: Screening Definition of BPD

Level of respiratory support at 36 weeks PMA	Eligibility
Room Air	Not Eligible (No or Mild BPD)
<2 L nasal cannula and <30% oxygen*	Eligible (Moderate BPD)
<2 L nasal cannula and >=30% oxygen**	Eligible (Severe BPD)
>=2 L nasal cannula or any positive pressure	Eligible (Severe BPD)

* <30% but receiving supplemental oxygen (22-29%) for at least 12 hours per day
** >=30% for 12 hours or more per day

3.3 Study Duration, Enrollment and Number of Sites

3.3.1 Duration of Study Participation

The study duration per subject will be up to 8 months, not including the screening and consent procedures. The baseline phase will last from the time of hospitalization until discharge, the

treatment phase and follow-up phase will take place during the time between discharge and the 6 month corrected age follow-up appointment.

Many of the children eligible for the study will be followed by the CHOP Chronic Lung Disease Program, which has both inpatient and outpatient components. In addition, all children will be eligible for routine care in the CHOP Neonatal Follow-up Program (NFP). It is anticipated that most outcomes assessments will be performed during routine pulmonary or NFP follow-up appointments. Growth parameters between 36 weeks PMA and 40 weeks PMA, 3 months CA, and 6 months CA will take place during scheduled follow-up appointments. Questionnaires will be collected at 3 and 6 months CA. All questionnaires will take approximately 15-30 minutes to complete.

3.3.2 Total Number of Study Sites/Total Number of Subjects Projected

Infants will be recruited from 3 neonatal intensive care units (NICUs): The Children's Hospital of Philadelphia (CHOP) NICU, the adjacent Hospital of the University of Pennsylvania (HUP) NICU, and Pennsylvania Hospital (PAH) NICU. All outpatient care will take place at CHOP. Up to 50 participants may be enrolled to reach our target sample of 42 patients with evaluable data.

3.4 Study Population

We will enroll male and female infants born less than 30 0/7 weeks at birth of all ethnicities who have been diagnosed with moderate or severe Bronchopulmonary Dysplasia; gender and race/ethnicity of the sample is expected to mirror the proportions of the Children's Hospital of Philadelphia, the Hospital of the University of Pennsylvania, and Pennsylvania Hospital patient populations. Subjects will be identified through EPIC. Because data about parent quality of life will be collected, subjects will be enrolled as parent-child dyads.

All inclusion and exclusion criteria will be reviewed by the investigator or qualified designee to ensure that the subject qualifies for the study.

3.4.1 Inclusion Criteria

- 1) Patient at CHOP,HUP, PAH (including both inborn and outborn infants)
- 2) Pre-term males or females infants born at <30 0/7 weeks gestation
- 3) Current age 34 0/7 to 43 6/7 weeks postmenstrual age
- 4) Diagnosis of moderate or severe Bronchopulmonary Dysplasia (as above)
- 5) Infant has never been discharged to home from the hospital

3.4.2 Exclusion Criteria

- 1) Family unlikely to be available for follow-up for 6 months
- 2) Congenital anomaly or oncologic process likely to affect growth or respiratory status
- 3) Hemoglobinopathy or other blood disorder likely to affect oxygen saturations
- 4) Contraindication to nasal cannula use (for example, severe nasal septal breakdown)

- 5) Pulmonary hypertension requiring pharmacotherapy at the time of screening/enrollment
- 6) Intubation at the time of screening/enrollment. (Infants may be approached while requiring higher levels of support, but may not enroll until extubation).
- 7) Tracheostomy
- 8) Parents/guardians or subjects who, in the opinion of the Investigator, may be non-compliant with study schedules or procedures

Subjects that do not meet all of the enrollment criteria may not be enrolled. Any violations of these criteria must be reported in accordance with IRB Policies and Procedures.

4 STUDY PROCEDURES

The Schedule of Study Procedures (Table 1) summarizes the study procedures to be performed at each point throughout the study. Individual study procedures are described in detail below.

4.1 Inpatient screening and enrollment

Data elements to be collected are listed in section 5.

4.2 Inpatient study procedures and data collection

Details of randomization are provided above in section 3.2.

4.2.1 Oxygen Saturation Monitoring

- While inpatient patients will have two monitors, a clinical monitor and a research monitor
- Alarm limits on the clinical monitor will be changed to reflect randomization assignment.
- Study oximeter will be placed on baby with the alarms off to ensure consistent data collection throughout.
- Orders in EPIC will be changed to reflect randomization

Data elements to be collected after enrollment and during the inpatient phase are listed in section 5. An interpreter will be used to administer questionnaires to non-English speaking subjects.

4.3 Outpatient study procedures and data collection

4.3.1 Oxygen Saturation Monitoring

- Prior to discharge, the family will receive a Masimo oximeter which will transmit data to the study team at CHOP.
- The study team will instruct the family how to use the oximeter correctly.
- The family will “teach back,” demonstrating that they understand correct use of the monitor.
- After discharge, the family will attach the probe to the toe and turn on the monitor each night while the child is in the crib. It will be disconnected and turned off in the morning, *unless* the child has been ordered for continuous home pulse oximetry by the discharging

physician. If clinical orders are for increased monitoring, the clinical orders will be followed.

- Oximetry data will be transmitted to the study team at CHOP nightly between discharge and 6 months CA.
- Each week the study team will review a report of the transmitted oximetry data.
- If the child is discharged on supplemental oxygen (based on clinical judgment), this will be weaned based on the child's assigned target saturation range and the study algorithm. This algorithm standardizes the typical approach to weaning used by the CHOP Division of Pulmonary Medicine. Downloaded data will be reviewed weekly and decisions about weaning will be made by the study team. In the home setting, weans may be performed as often as every week. If an infant loses >5% of body weight in any month, no oxygen weans will be made until the weight is regained. If an infant is discharged without oxygen or weans off but then meets the criteria for increasing flow on two subsequent recordings, the family will be instructed to attend pulmonary clinic for assessment and then home oxygen therapy will be instituted.
- Families will be instructed how to evaluate the infant in the case of an alarm, just as with home clinical monitoring. If the infant is kicking/moving and the alarm seems related to motion, they will ensure that the probe is well secured and follow for further events. If the alarms are recurrent and the infant has respiratory distress, response will differ based on the infant's situation: If the child is on oxygen, the family will be instructed to turn up the oxygen and call the pulmonary team. If the child is not on oxygen and has mild distress or cold symptoms, they will be instructed to call the pediatrician. All children with severe respiratory distress and persistent low alarms should go to the emergency room. This is all consistent with the instructions given to all families of children with BPD at the time of discharge from the neonatal hospitalization.

4.3.2 Study outcomes and safety data

Nearly all participants will have a clinical visit with either the Neonatal Follow-up Program, the Chronic Lung Disease Program, or the Pulmonary clinic at about 3 months corrected age. If none of these are scheduled, a visit at the CTRC will be arranged. If this is not possible, the PI will arrange a home visit with the family. The 3 month assessments can be conducted in any of these locations. Specific data elements to be collected during these clinical or study visits are listed in section 5.

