4.4 Unscheduled Visits

It is likely that the participant will have interim clinical visits to the Neonatal Follow-up Program, Pulmonary clinic, and the pediatrician. Wherever possible, study visits will be arranged to align with these visits.

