5.1.4 Outpatient Data Collection

During the remainder of the study period, the following data will be collected:

- Rehospitalizations: location, duration, and ICU care, primary reason for hospitalization
- Medication use
- Visits to doctor or emergency room, with reason
- Procedures or surgeries
- Growth parameters as assessed at any clinical visit(s)
- Mode of feeding
- Developmental assessment (Bayley screener)

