5.2.2 Efficacy Evaluations: Clinical

In this pilot study, physiologic (oximetry) data are the primary outcomes. All clinical outcomes/assessments of efficacy are exploratory and descriptive. Methods and timing of measures that will be used to assess efficacy are:

Primary Clinical Outcome:

Growth in kilograms between 36 weeks PMA and 6 months CA as well as other growth parameters.

- Change in Length (cm)
- Weight for length
- Head circumference (cm)

Secondary Clinical Outcomes:

- Feeding questionnaire: The questions that will be asked at 3 and 6 months are selected to assess feeding skills and estimate caloric intake. The questions are selected from longer questionnaires administered as part of the Millennium Birth Study, with permission from the author of the original study.(13)
- The ITQOL---SF47- Parent and child quality of life survey: The Infant Toddler Quality of Life Questionnaire™ (ITQOL) was developed for use in infants and toddlers at least 2 months of age up to 5 years. The Infant Toddler Quality of Life Questionnaire™ (ITQOL) adopts the World Health Organization's definition of health, as a state of complete physical, mental and social wellbeing and not merely the absence of disease. The survey was developed following a thorough review of the infant health literature and a review of developmental guidelines used by pediatricians. The ITQOL includes questions that assess the impact of health on both child and parent quality of life.
- Medical resource utilization recorded at 3 and 6 months corrected age: medications (including dose, route, frequency, and indication), doctor and emergency room visits, hospitalizations (whether or not in ICU, duration, and indication), therapies (type and frequency), and home equipment use. These data will be extracted from the EMR wherever possible and verified with the participant's parent(s).
- Development: Per standard of clinical care, the Bayley Scales of Infant Development- 3rd Edition Screening Test is administered to all children who attend the Neonatal Follow-up Program (NFP) at 6 months corrected age. (All children eligible for this study will be

followed at the NFP per standard of care) Results of this clinical evaluation will be recorded for the study.

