6.4 Sample Size and Power

No preliminary data about incidence of IH in infants with moderate or severe BPD are available. Therefore, our sample size is based on extrapolations from the existing studies. Rhein reported 8.2 +/- 11.5 events of 5 seconds or longer per hour (197 per day) at 36 weeks PMA.(8) Poets reported a median 88.4 events of 10 seconds or longer per day in the Canadian Oxygen Trial.(7) We assume that fewer than half of these will be longer events that meet our study definition of IH, and estimate that our study participants will have between 20-30 IH events per 8-hour period at baseline. We plan to recruit 42 participants with useable data, which will provide sufficient power to detect a relative reduction of 30% between the high and low SpO₂ target groups if the baseline rate is 30 events per 8 hours. Therefore, our target sample size is 42 children *with complete data*.

Mean weight at 36 weeks PMA based on the Olsen growth curves is 2.8 kg,(14) and mean weight at 6 months CA based on the WHO growth curves is 7.9 kg.(15) Therefore, we assume a mean growth of 5.1 kg in the higher SpO₂ group and less weight gain in the lower SpO₂ group. The target sample size of 42 children will provide >80% power to detect a mean difference in growth of 0.5kg between the two study groups.

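### The back-up visit arrangements cover the 3-month assessment only, and 6-month weight gain is analysed in raw kilograms with no visit window and no adjustment for age at weighing

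*Combined protocol and SAP*

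**What the plan says.** Section 4.3.2 describes where the 3-month data will be obtained. Most infants are expected to attend one of three clinics, the last being "or the Pulmonary clinic at about 3 months corrected age. If none of these are scheduled, a visit at the CTRC will be arranged". After that: "If this is not possible, the PI will arrange a home visit with the family". The paragraph closes with "The 3 month assessments can be conducted in any of these locations". The trigger is that no clinic visit is scheduled. The protocol has no matching paragraph for 6 months.

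The main route to the 6-month data is standard of care. Section 3.1.4 says that "participants will be evaluated in the CHOP Neonatal Follow-up Program at 3 and 6 months corrected ages". Four other sections help:

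- Section 3.3.1 expects most outcomes to be assessed at routine pulmonary or Neonatal Follow-up Program appointments.
- Section 4.3.3 promises 3- and 6-month data for infants who stop monitoring early.
- Section 4.6 keeps infants who miss appointments in the study.
- Section 5.1.4 collects growth from any clinical visit.

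The primary clinical outcome in Section 5.2.2 is "Growth in kilograms between 36 weeks PMA and 6 months CA as well as other growth parameters". Section 6.2 repeats it and labels all secondary endpoints exploratory. Section 6.3.2 plans generalized estimating equations for growth and lists six candidate covariates. Age at measurement is not one of them. Section 6.4 states: "The target sample size of 42 children will provide >80% power to detect a mean difference in growth of 0.5kg between the two study groups". It gives no SD, alpha or sidedness.

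**The concern.** The gap is at the visit that matters most for the clinical outcomes. The 6-month visit supplies the endpoint of the primary clinical outcome, the second set of questionnaires and the only Bayley screener. Yet the written back-up applies to the earlier visit. None of the four partial protections says where a 6-month weight will be taken if no appointment exists or one is missed. None says which other weight may stand in for it.

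The second issue is the scale. Infants gain weight throughout this period, so an infant weighed late appears better grown than the same infant weighed on time. With raw kilograms, no window and no age term, differences in visit age go straight into the outcome's variance. Section 6.3.2 says these analyses are meant to help plan later studies, and a growth SD inflated by appointment timing would carry over into that planning. Growth also serves as a safety measure in Section 6.2.

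**Working it through.** **Inputs from the documents.** The target difference is 0.5 kg, with more than 80% power and 42 children (Section 6.4). Blocks of 2 or 4 (Section 3.2) imply equal allocation, so 42/2 = 21 per arm. Mean gain is 7.9 − 2.8 = 5.1 kg (Section 6.4). The interval from 36 weeks PMA to 6 months corrected age is about 4 + 26 = 30 weeks, so the average gain is 5.1/30 = 0.17 kg/week.

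**Assumptions, because the documents are silent.** The test is two-sided at 5%. The SD of weight gain at exact age is 0.50 kg, or the largest value the power statement allows. Visit ages are spread evenly over ±h weeks, which gives an SD of h/√3 weeks. Weight velocity near 6 months is either the interval average of 0.17 kg/week or a slower 0.10 kg/week. The true value is probably below the average and is not given.

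**Step 1: the plan's own figure.** Without an SD, the power statement cannot be reproduced forwards. Solved backwards with a two-sample t test at 21 per arm, 80% power needs a standardized difference of 0.886, so SD = 0.5/0.886 = 0.564 kg. The normal approximation gives (1.960 + 0.842) × √(2/21) = 0.865, so SD = 0.5/0.865 = 0.578 kg. The statement therefore requires a total SD of at most about 0.56 to 0.58 kg. A one-sided test would allow about 0.64 kg (t).

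**Step 2: add timing spread.** Total SD = √(SD² + (velocity × h/√3)²). For SD 0.50, 0.17 kg/week and ±2 weeks, the timing part is 0.17 × 1.155 = 0.196 kg. The total is √(0.2500 + 0.0385) = 0.537 kg and power is 83.7%. The other cases follow in the same way (t test, 21 per arm):

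| SD at exact age | Velocity (kg/week) | No spread | ±2 weeks | ±4 weeks |
|---|---|---|---|---|
| 0.50 kg | 0.17 | 88.5% | 83.7% | 70.1% |
| 0.50 kg | 0.10 | 88.5% | 86.9% | 81.9% |
| 0.564 kg | 0.17 | 80.0% | 75.4% | 63.3% |
| 0.564 kg | 0.10 | 80.0% | 78.4% | 73.7% |

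**Step 3: how much spread the plan can absorb.** Starting from 0.50 kg, the 80% limit is reached when timing adds √(0.564² − 0.50²) = 0.26 kg of SD. That is a visit-age SD of 0.26/0.17 = 1.5 weeks, or 0.26/0.10 = 2.6 weeks.

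**Step 4: missing 6-month weights.** Enrolling up to 50 for 42 evaluable allows 1 − 42/50 = 16% loss. If fewer than 42 weights are obtained:

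| Children with a 6-month weight | Power, SD 0.50 kg | Power, SD 0.564 kg |
|---|---|---|
| 42 | 88.5% | 80.0% |
| 38 | 85.1% | 75.7% |
| 34 | 80.7% | 70.7% |

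**The case against.** The strongest reply is that the 6-month weight is better protected than Section 4.3.2 alone suggests. That is right as far as it goes. A reader might infer that it depends on the Neonatal Follow-up Program appointment alone. The documents do not support this, since Section 3.3.1 also names pulmonary appointments and Section 5.1.4 takes growth from any clinical visit. What remains missing is a named back-up location and a rule for choosing a substitute weight. The 3-month back-up is itself narrow, because it answers visits that were never scheduled and does not mention missed ones.

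The evidence on timing is also indirect. The wording about approximate age belongs to the 3-month visit. Section 4.4, where "Wherever possible, study visits will be arranged to align with these visits", concerns interim visits. The 6-month assessment is consistently set at 6 months corrected age. So the documents do not show that infants will be weighed at widely varying ages; they show only that no window limits the variation.

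A reader might also infer that the outcome is too noisy for its 0.5 kg target. This cannot be shown. Starting from the largest SD compatible with exactly 80% makes any added variance fall below 80% by construction, whereas the plan claims more than 80%. The planners' SD may also already include timing spread. Several rows in the working stay above 80%.

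Nor does it follow that a weighing 3 weeks late cancels the target, although 0.5/0.17 is about 2.9 weeks. That figure applies the interval average at 6 months and concerns one infant. A bias of that size would need a systematic 3-week gap between the arms. Nothing in the documents indicates that visit timing or missing weights will differ by arm.

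Finally, this is a pilot whose primary outcomes are oximetric. That limits the weight of the point but does not remove it.

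**Conclusion.** The point holds in a limited form. Two omissions are confirmed: no back-up wording for the visit that carries the endpoint of the primary clinical outcome, and no window, age term or standardized score for a raw-kilogram outcome measured at appointments. The result is avoidable variance and some avoidable risk of missing weights.

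The size is conditional. With SD 0.50 kg at exact age, the loss is about 2 to 5 percentage points of power for visits within ±2 weeks (88.5% to 86.9% or 83.7%). Within ±4 weeks it is about 7 to 18 points (to 81.9% or 70.1%). The lower figure in each range uses the assumed 0.10 kg/week and the higher the 0.17 kg/week average. All of this rests on the assumed SD, alpha and even spread of visit ages. It is a minor-to-moderate point, worth acting on mainly because the remedy costs so little.

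**What to change.** - **Section 4.3.2:** extend the existing CTRC and home-visit wording to the 6-month weight, length, head circumference and questionnaires. Let it apply when a visit is missed as well as when none is scheduled.
- **Sections 5.2.2 and 6.3.2:** record the date of every growth measurement. Include exact corrected age at measurement as a prespecified covariate in the growth model, exempt from the rule that covariates enter only if the groups differ significantly. Alternatively, analyse age- and sex-standardized z-scores at exact age and report kilograms alongside.
- **Substitute weights:** when the 6-month visit is missed, use the nearest clinical weight collected under Section 5.1.4, within a window stated in advance and applied identically in both arms.

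The cost is a few wording changes, one model term and a small number of extra weigh-ins under arrangements the protocol already has. Stating the SD, alpha and sidedness behind the power claim in Section 6.4 would also let the size of this point be settled.
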